2.8.1.1 AEs of special interest / grouping of AEs

Not applicable.

2.8.2 Deaths

The primary reason for death will be summarized by system organ class and preferred term. All deaths will be listed. Deaths for screen failures will be listed separately.

2.8.3 Laboratory data

Hematology, clinical chemistry, and fasting laboratory tests parameter will be summarized with standard descriptive statistics by visit, overall and by subpopulation presenting the baseline value, post-baseline value and change from baseline. Change from baseline will only be summarized for subjects with both baseline and post-baseline values.

For each parameter, the maximum change (maximum decrease and maximum increase) from baseline will be analyzed analogously.

Shift tables will be provided for all parameters to compare a patient's baseline laboratory evaluation relative to the worst observed value during the treatment phase. For the shift tables, the normal laboratory ranges will be used to evaluate whether a particular laboratory test value was normal, low, or high for each visit value relative to whether or not the baseline value was normal, low, or high. These summaries will be presented by laboratory test overall and by subpopulation. Shifts will be presented by visit and for most extreme values post-baseline.

For urinalysis dipstick results a frequency table will be produced by parameter and visit.

The following laboratory parameters will be analyzed with respect to numerical Common Terminology Criteria for Adverse Events (CTCAE) grades, given in [Appendix 5.3](#): hemoglobin, platelets, white blood cell count, neutrophils, lymphocytes, creatinine, total bilirubin (TBL), gamma-glutamyl transferase (GGT), alanine aminotransferase (ALT), aspartate aminotransferase (AST), alkaline phosphatase (ALP).

The number and percentage of patients with CTCAE grade newly occurring or worsening after baseline will be presented. These summaries will be split into hematology and chemistry.

Shift tables will be presented comparing baseline laboratory result (CTCAE grade) with the worst results (expressed in CTCAE grade) post-baseline.

For a patient to meet the criterion of a newly occurring clinically notable value, the patient needs to have a baseline value which is not clinically notable for that parameter. For a patient to meet the criterion of a worsening clinically notable value, the patient needs to have a baseline value which is clinically notable and also have a worse post-baseline value.

Listings of patients with laboratory values meeting CTCAE grades will be provided by treatment group, patient, and laboratory parameter.

Serum and urine pregnancy test results will be listed only.

Liver function tests (LFT)

To evaluate potential drug-induced liver injury, the number and percentage of patients with newly occurring or worsening abnormalities in liver function tests at any time post-baseline will be summarized by treatment based on the following criteria:

Table Notable liver function test values

Criterion
ALT > 3 x the upper limit of normal range (ULN) ALT > 5 x ULN ALT > 8 x ULN ALT > 10 x ULN ALT > 20 x ULN
AST > 3 x ULN AST > 5 x ULN AST > 8 x ULN AST > 10 x ULN AST > 20 x ULN
ALT or AST > 3 x ULN ALT or AST > 5 x ULN ALT or AST > 8 x ULN ALT or AST > 10 x ULN ALT or AST > 20 x ULN
Total bilirubin > 1.5 x ULN Total bilirubin > 2 x ULN Total bilirubin > 3 x ULN
ALP > 2 x ULN ALP > 3 x ULN ALP > 5 x ULN
ALT or AST > 3 x ULN and total bilirubin > 2 x ULN ALT or AST > 5 x ULN and total bilirubin > 2 x ULN ALT or AST > 8 x ULN and total bilirubin > 2 x ULN ALT or AST > 10 x ULN and total bilirubin > 2 x ULN
ALP > 3 x ULN and total bilirubin > 2 x ULN ALP > 5 x ULN and total bilirubin > 2 x ULN
ALT or AST > 3 x ULN and Total Bilirubin > 2 x ULN and ALP < 2 x ULN (Hy's law)

ALT = alanine aminotransferase, AST = aspartate aminotransferase, ALP = alkaline phosphatase

When a criterion contains multiple laboratory parameters, the criterion will only be considered to have been met when all conditions occur at the same time (i.e., within the same sample). A case where all criteria are met at a post-baseline time point will be considered as newly occurring if the criteria are not met at baseline and will be considered as worsening if the criteria are met at baseline and at least one component is worsening from baseline irrespective of whether the other(s) are better.

Listings of patients with clinically notable LFT values will be provided.

2.8.4 Other safety data

2.8.4.1 ECG and cardiac imaging data

No ECG data are collected in this study.

2.8.4.2 Vital signs

Vital signs (blood pressure, pulse rate, weight, waist circumference and hip circumference) will be summarized with standard descriptive statistics by visit, overall and by subpopulation presenting the baseline value, post-baseline value and change from baseline.

Newly occurring notable values for vital signs will be summarized. Notable values are defined as

- Systolic blood pressure (mmHg) ≥ 140 mmHg or < 90 mmHg
- Diastolic blood pressure (mmHg) ≥ 90 mmHg or < 60 mmHg
- Pulse (bpm) > 100 bpm or < 60 bpm

Data of subjects with newly occurring notable vital signs abnormalities will be listed in an additional listing.

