 - Use of established oral, injected or implanted hormonal methods of contraception, intrauterine device or intrauterine system post-ovulation methods).

NOTE: Women are considered post-menopausal and not of child bearing potential if they have had:

- 12 months of natural (spontaneous) amenorrhea with an appropriate clinical profile (e.g. age appropriate, history of vasomotor symptoms) or
 - 6 months of spontaneous amenorrhea with serum FSH levels > 40 mIU/mL [for US only: and estradiol < 20 pg/mL] or
 - Surgical bilateral oophorectomy (with or without hysterectomy) or tubal ligation at least 6 weeks before taking study treatment. In case of oophorectomy alone, only when the reproductive status of the woman has been confirmed by follow-up hormone level assessment is she considered not of child bearing potential.
5. Active ongoing inflammatory diseases other than psoriasis that might confound the evaluation of the benefit of secukinumab therapy.
 6. Underlying condition (including but not limited to metabolic, hematologic, renal, hepatic, pulmonary, neurologic, endocrine, cardiac, infectious or gastrointestinal), which in the opinion of the Investigator significantly immunocompromises the patient and/or places the patient at unacceptable risk for receiving an immunomodulatory therapy. Patients who are treated with secukinumab and have Crohn's disease are eligible but should be followed closely.
 7. Investigator discretion should be used for patients with preexisting or recent-onset central or peripheral nervous system demyelinating disorders.
 8. Significant medical problems including but not limited to the following: uncontrolled hypertension (systolic ≥ 160 mmHg and/or diastolic ≥ 95 mmHg), congestive heart failure (New York Heart Association (NYHA) status of class III or IV).
 9. Patients with a serum creatinine level exceeding 176.8 $\mu\text{mol/L}$ (2.0 mg/dL).
 10. Screening total white blood cell (WBC) count < 2 500/ μL , or platelets < 100 000/ μL or neutrophils < 1 500/ μL or hemoglobin < 8.5 g/dL.

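### The notable vital-sign table and its extra listing count only newly occurring values, so further worsening of a parameter already notable at baseline is not shown there

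*SAP*

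**What the plan says.** SAP 2.8.4.2 plans two kinds of vital-sign output. One is by-visit descriptive statistics with change from baseline, overall and by subpopulation. The other covers notable values: "Newly occurring notable values for vital signs will be summarized", followed by "Data of subjects with newly occurring notable vital signs abnormalities will be listed in an additional listing".

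Each parameter has one criterion holding both a high and a low limit. For systolic pressure it is "Systolic blood pressure (mmHg) ≥ 140 mmHg or < 90 mmHg". The diastolic criterion is built the same way, with notable values from 90 upwards or under 60, and so is the pulse criterion, with notable values over 100 or under 60.

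The section does not define newly occurring, has no worsening category and gives no denominator.

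SAP 2.8.3 handles graded laboratory values differently: "The number and percentage of patients with CTCAE grade newly occurring or worsening after baseline will be presented". There, newly occurring means that "the patient needs to have a baseline value which is not clinically notable for that parameter", and a separate worsening rule covers patients who start notable and get worse. Liver tests are also reported as new or worsening.

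On entry, exclusion criterion 8 in Protocol 4.2 rules out "uncontrolled hypertension (systolic ≥ 160 mmHg and/or diastolic ≥ 95 mmHg").

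**The concern.** Between the notable limits (140/90) and the exclusion limits (160/95) lies a band of eligible patients: SBP 140-159 or DBP 90-94. They meet the notable criterion before the first dose. A table restricted to new occurrences has no place for a further rise in the same parameter. It counts a change from 138 to 142 and leaves out one from 142 to 190.

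Two smaller issues follow. First, because high and low limits share one criterion, a swing to the opposite extreme may also go uncounted, depending on how newly occurring is read. Second, if already-notable patients stay in the denominator, the reported percentage falls as baseline prevalence rises.

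What is at stake is the completeness of the only categorical vital-sign safety output, which is to be presented for subpopulations A, B and C and overall.

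**Working it through.** **No plan figure to reproduce.** The documents attach no number to this rule, so the check applies the stated limits to example changes and then sizes the gap under assumptions.

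**Step 1: three readings of the rule.** Inputs are the limits in SAP 2.8.4.2.

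- (a) New, high and low joined: notable after baseline and not notable in either direction at baseline. This carries over the laboratory definition.
- (b) New, by direction: high after baseline and not high at baseline, or low after baseline and not low at baseline.
- (c) New or worsening, by direction: (b), plus patients already high who go higher or already low who go lower.

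| Change from baseline | (a) | (b) | (c) |
|---|---|---|---|
| SBP 138 to 142 | counted | counted | counted |
| SBP 142 to 180 | no | no | counted |
| SBP 150 to 200 | no | no | counted |
| DBP 92 to 115 | no | no | counted |
| Pulse 104 to 140 | no | no | counted |
| Pulse 58 to 45 | no | no | counted |
| SBP 150 to 85 | no | counted | counted |
| DBP 92 to 55 | no | counted | counted |
| Pulse 58 to 130 | no | counted | counted |

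Every integer baseline SBP from 140 to 159 was paired with every post-baseline SBP from 50 to 259. Reading (a) never counts the patient for SBP. Reading (b) counts them only when SBP falls below 90, never for a further rise.

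So the same-direction gap appears under both (a) and (b): it comes from the missing worsening category. The joined limits add only the opposite-direction gap, and only under (a).

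**Step 2: denominator.** SAP 2.1 computes percentages on the number of patients in the relevant population or subgroup, and SAP 2.8.4.2 states no exception. Let b be the share already notable at baseline and r the risk of a new notable value among the rest. The reported percentage is then r × (1 − b). With an illustrative r = 20%:

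- b = 14%: 20% × 0.86 = 17.2%
- b = 28%: 20% × 0.72 = 14.4%

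The 2.8-point difference arises although the risk among at-risk patients is the same.

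**Step 3: how many patients.** The documents give no baseline blood pressure distribution. All of the following are assumptions: bivariate normal SBP and DBP, means from 126/78 to 134/82, SD 14-15 and 9-10, correlation 0.6, truncated below 160 and 95 to mimic criterion 8. Simulated shares notable at baseline because SBP is at least 140 or DBP at least 90:

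| | Means 126/78 | Means 134/82 |
|---|---|---|
| SBP | about 14% | about 28% |
| DBP | about 6% | about 12% |
| Both | about 3% | about 7% |
| Either | about 17% | about 33% |

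Of the planned 1,615 patients, 14% to 28% is about 226 to 452 for SBP (0.14 × 1,615 and 0.28 × 1,615). Notable on both is about 48 to 113 (0.03 × 1,615 and 0.07 × 1,615). These are patients whose further rise could not be counted, not patients expected to worsen.

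**The case against.** The strongest reply is that little is hidden. The by-visit statistics include minimum, third quartile and maximum (SAP 2.1), so an extreme value or change would show there. Protocol 9.5.2 has all vital signs listed by group, patient and time, and the SAP calls its own notable listing additional. A rise judged to be an adverse event enters the adverse event tables. Protocol 9.5.2 asks for no notable-value table, so the SAP already goes further than required, and counting only new onset is an ordinary choice for an incidence table. The analyses are descriptive with no formal group comparison.

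Most of this stands, and it limits the point. It does not remove it. By-visit summaries do not count patients, a full listing is not a summary, and adverse event reporting of a reading depends on the investigator's judgement. The SAP also gives no reason for treating vital signs differently from laboratory values.

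Two stronger readings are tempting and are not supported:

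- *A reader might infer that patients who enter hypertensive can never be flagged.* The restriction works per parameter. A patient at 145/82 can still be counted for DBP or pulse. The 17% to 33% notable on either blood pressure measure therefore overstates those shut out of any count for a rise in blood pressure; notable on both is about 3% to 7% under the same assumptions.
- *A reader might infer that joining high and low limits is what hides further rises.* Step 1 shows it is not. Even the opposite-direction gap depends on borrowing the laboratory definition. Protocol 6.5.2 names hypertension and hypotension, and bradycardia and tachycardia, separately, so SBP 150 to 85 could fairly be read as new hypotension.

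**Conclusion.** The point holds in a limited form. For a parameter already notable at baseline, further worsening in the same direction cannot appear in the notable-value table or its additional listing. This follows from any ordinary reading of newly occurring and is inconsistent with SAP 2.8.3. The opposite-direction gap is conditional on the laboratory definition being carried over. The dilution of percentages is conditional on the general denominator rule of SAP 2.1 being applied to this table.

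The number affected is unknown; the shares in the working rest wholly on assumed distributions. This is a minor gap in descriptive safety reporting. Nothing in the documents suggests an effect on the primary analysis, on data collection or on the monitoring of individual patients.

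**What to change.** In SAP 2.8.4.2:

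1. Define newly occurring separately for high and low values of SBP, DBP and pulse. Use as denominator the patients who are not notable in that direction at baseline and have a post-baseline value.
2. Add a worsening category on the model of SAP 2.8.3, or a low/normal/high shift table from baseline to the most extreme post-baseline value. The worsening category is the more direct remedy. In a shift table, SBP 142 to 190 falls in the high-to-high cell together with patients who did not change, so it relies on item 3 to show the size of the rise.
3. Include worsening patients in the additional listing, with baseline and most extreme values side by side.

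Severity bands at 160/95 are not needed; those figures are eligibility limits, and Protocol 6.5.2 does not use them to grade vital signs.

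The cost is SAP wording and one extra table, from data already collected.

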2.9 Pharmacokinetic endpoints

Not applicable.

2.10 PD and PK/PD analyses

[figure not shown]
Not applicable.

[figure not shown]
2.11 Patient-reported outcomes

[figure not shown]
See [Section 2.5](#) for primary endpoint and [Section 2.7](#) for secondary endpoints as well as [Section 2.13](#) for other exploratory analysis.

2.12 Biomarkers

If a biomarker substudy is performed, details will be described in a separate study protocol and SAP.

2.14 Interim analysis

An interim analysis describing the self-reported baseline characteristics and HR-QoL of patients prior to treatment will be performed for this study after LPFT.

The interim analysis will be based on the Safety set.

Patient screening phase disposition, demographics, baseline disease characteristics, baseline IGA mod 2011, PASI and PROs will be presented as described in [Section 2.3](#).

Other medical history and prior medications and non-drug therapies will not be part of the interim analysis.

3 Sample size calculation

The study aims to estimate primarily the effect of 16 weeks treatment with secukinumab 300 mg on the QoL of the overall study population as well as within the 3 pre-defined subpopulations. It is expected that 40% of the overall study population will fulfil the criteria

for the definition of subpopulation A; 40% will fulfil the criteria for subpopulation B; and 20% will fulfil the criteria for subpopulation C.

The DLQI 0/1 response rate in the overall population treated with secukinumab 300 mg s.c. is expected to be around 70% at Week 16; however, it may vary within those pre-defined subpopulations. A total of 323 patients are required to estimate the response rate of DLQI 0/1 with a precision (= 95% CI) of 5% if the true response rate is about 70% in the smallest subpopulation. To ensure that this precision is achieved in the 3 subpopulations (defined in Section 3.1), which consist of 20% to 40% of the overall study population, 1 615 patients in total should be recruited into this trial.

4 Change to protocol specified analyses

According to the protocol all data from physical examinations should be summarized and listed. As these data are only collected in the source data (see Section 6.5.1 of the protocol) this will not be analyzed.

5 Appendix

5.1 Imputation rules

5.1.1 Study drug

Not applicable.

5.1.2 AE date imputation

Not applicable as complete dates for AEs must be reported in the eCRF.

5.1.3 Concomitant medication date imputation

Rules for imputing the prior/concomitant medication (CMD) start date:

1. If the CMD start date year value is missing, the imputed CMD start date is set to one day prior to treatment start date, if not after the CMD end date. Thus the imputed CMD start date will be the minimum of one day prior to treatment start date and the CMD end date.
2. If the CMD start date year value is less treatment start date year value, the CMD started before treatment start. Therefore:
 - a) If the CMD year is less than treatment start year and the CMD month is missing, the imputed CMD start date is set to 01JulYYYY.
 - b) Else if the CMD year is less than the treatment start year and the CMD month is not missing, the imputed CMD start date is set to 15MONYYYY.
3. If the CMD start date year value is greater than treatment start date year value, the CMD started after treatment start. Therefore:

- a) If the CMD year is greater than the treatment start year and the CMD month is missing, the imputed CMD start date is set to 01JanYYYY.
 - b) Else if the CMD year is greater than the treatment start year and the CMD month is not missing, the imputed CMD start date is set to 01MONYYYY.
4. If the CMD start date year value is equal to treatment start date year:
- a) If the CMD month is missing or the CMD month is equal to treatment start month, then the imputed CMD start date is set to the minimum of one day prior to treatment start date and the CMD end date.
 - b) Else if the CMD month is less than the treatment start month, the imputed CMD start date is set to 15MONYYYY.
 - c) Else if the CMD month is greater than the treatment start month, the imputed CMD start date is set to 01MONYYYY.

Rules for imputing the CMD end date:

1. If the CMD end date is completely missing (and "Ongoing at final examination" was not answered "Yes"), the CMD end date will be the maximum of treatment end date + 1 day and CMD start date.
2. If a partial CMD end date is reported (day is missing or day and month are missing), the CMD end date will be imputed by the maximum possible date, i.e., the end of the reported month if day is missing, or the end of the reported year if day and month are missing provided that the imputed date is not before the CMD start date, otherwise CMD end date will be equal to CMD start date.

5.2 AEs coding/grading

AEs are coded using the Medical dictionary for regulatory activities (MedDRA) terminology.

5.3 Laboratory parameters derivations

The following table shows the CTCAE grades for laboratory parameter. Not all parameters have CTCAE grades defined.

CTCAE Term	Grade 1	Grade 2	Grade 3	Grade 4
HGB decreased (Anemia)	<LLN - 100 g/L	<100 - 80 g/L	<80 g/L	-
Platelet count decreased	<LLN - 75.0 x10e9 /L	<75.0 - 50.0 x10e9 /L	<50.0 - 25.0 x10e9 /L	<25.0 x 10e9 /L
White blood cell decreased	<LLN - 3.0 x 10e9 /L	<3.0 - 2.0 x 10e9 /L	<2.0 - 1.0 x 10e9 /L	<1.0 x 10e9 /L
Neutrophil count decreased	<LLN - 1.5 x 10e9 /L	<1.5 - 1.0 x 10e9 /L	<1.0 - 0.5 x 10e9 /L	<0.5 x 10e9 /L
Lymphocyte count decreased	<LLN - 0.8 x 10e9/L	<0.8 - 0.5 x 10e9 /L	<0.5 - 0.2 x 10e9 /L	<0.2 x 10e9 /L
Creatinine increased	>ULN - 1.5 x ULN	>1.5 - 3.0 x ULN	>3.0 - 6.0 x ULN	>6.0 x ULN
TBL increased	>ULN - 1.5 x ULN	>1.5 - 3.0 x ULN	>3.0 - 10.0 x ULN	>10.0 x ULN
GGT increased	>ULN - 2.5 x ULN	>2.5 - 5.0 x ULN	>5.0 - 20.0 x ULN	>20.0 x ULN
ALT increased	>ULN - 3.0 x ULN	>3.0 - 5.0 x ULN	>5.0 - 20.0 x ULN	>20.0 x ULN
AST increased	>ULN - 3.0 x ULN	>3.0 - 5.0 x ULN	>5.0 - 20.0 x ULN	>20.0 x ULN
ALP increased	>ULN - 2.5 x ULN	>2.5 - 5.0 x ULN	>5.0 - 20.0 x ULN	>20.0 x ULN

5.4 Derivation of index values and scores

5.4.1 DLQI

The **DLQI**[®] is a 10-item general dermatology disability index. Each item has 4 response categories ranging from "not at all" to "very much". "Not relevant" is also a valid response. The scoring for each question is as follows:

Response	Score
Very much	3
A lot	2
A little	1
Not at all	0
Not relevant	0
Question unanswered	0
Question 7: "prevented work or studying" is answered as "Yes"	3
Question 7: "prevented work or studying" is answered as "No" and "problem at working or studying" is answered as "A lot"	2
Question 7: "prevented work or studying" is answered as "No" and "problem at working or studying" is answered as "A little"	1
Question 7: "prevented work or studying" is answered as "No" and "problem at working or studying" is answered as "Not at all", "Not relevant" or unanswered.	0

The DLQI is calculated by summing the score of each question resulting in a maximum of 30 and a minimum of 0. The higher the score, the more quality of life is impaired. If more than one question left unanswered the score will not be calculated and set to missing.

The DLQI 0/1 response is defined as a DLQI total score of 0-1.

The DLQI subsection scores will be calculated as by summing the scores of specific questions as follows:

Subsection	Questions	Maximum Score
Symptoms and feelings	Questions 1 and 2	6
Daily activities	Questions 3 and 4	6
Leisure	Questions 5 and 6	6
Work and school	Question 7	3
Personal relationships	Questions 8 and 9	6
Treatment	Question 10	3

The DLQI subsection response of 0 is defined as a DLQI subsection score of 0.

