2.5.3 Handling of missing values/censoring/discontinuations

The last observation carried forward (LOCF) method will be applied to the continuous variables of DLQI score that are missing after baseline regardless to the reason for missing data (e.g. premature study discontinuation, missed visit, administrative issues). The binary response variable based on DLQI score will be derived from these imputed values, this means that a patient with missing values will be counted as a non-responder unless he already achieved the respective response criterion at the last available measurement. Baseline values will not be carried forward. LOCF will be applied to all post-baseline visits.

LOCF imputation:

1. Assign analysis visit windows as described in [Section 2.1.1](#) per assessment date for unscheduled visits.
2. If no eCRF visit is assigned to an analysis visit as per [Section 2.1.1](#), impute with LOCF

Any missing individual items are treated as missing data. Handling of missing items within the DLQI questionnaire is described in the [Appendix 5.4.1](#).

The percentage of missing items in the DLQI questionnaire and will be presented over visits. In addition the percentage of scores/index values imputed with LOCF will be presented by visit.

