2.7.2.1 DLQI

The absolute and relative frequencies (including 95% CI) of patients achieving a DLQI 0/1 response will be presented by visit, overall and by subpopulation. The proportion of DLQI 0/1 response will be presented graphically over visits.

The absolute and relative frequencies (including 95% CI) of patients achieving a 0 response in a subsection will be analyzed similarly to the DLQI 0/1 response separately for each subsection.

The number and percentages (including 95% CI) of patients in each DLQI score category of 0-1, 2-5, 6-10, 11-20, 21-30 will be presented by visit, overall and by subpopulation. In

addition a shift table using these categories will be presented to compare baseline and Week 16/Week 52 respectively.

The DLQI score and the DLQI subsection scores will be summarized by visit, overall and by subpopulation presenting the baseline value, post-baseline value, change from baseline and percent change from baseline.

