2.7.3 Handling of missing values/censoring/discontinuations

The last observation carried forward (LOCF) method will be applied to all secondary variables.

Any missing individual items will not be imputed. Handling of missing items within each questionnaire is described in the [Appendix 5.4](#).

For each questionnaire, where it is allowed to skip questions (DLQI, HAQ-DI, PBI, TSQM [REDACTED]), the percentage of missing items and will be presented over visits. In addition the percentage of scores/index values imputed with LOCF will be presented by visit.

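### SAP 5.4.1 scores a skipped DLQI question as 0 and has no missing rule for the subsections, so a skipped question can count as a subsection response

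*SAP*

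**What the plan says.** The scoring table in SAP 5.4.1 has a row "Question unanswered" with score 0, equal to the scores for the least-affected answer and for a not-relevant answer. The ten item scores are summed to the 0–30 total, and one missing rule follows: "If more than one question left unanswered the score will not be calculated and set to missing".

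The subsections come after that rule: "The DLQI subsection scores will be calculated as by summing the scores of specific questions as follows". Four have two questions each (1–2, 3–4, 5–6, 8–9) and two have one (Work and school is question 7; Treatment is question 10). No missing rule is attached to them. The section ends: "The DLQI subsection response of 0 is defined as a DLQI subsection score of 0".

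SAP 2.7.2.1 puts these responses into the secondary reporting: "The absolute and relative frequencies (including 95% CI) of patients achieving a 0 response in a subsection will be analyzed similarly to the DLQI 0/1" total-score response, for each subsection. It also summarises subsection scores at baseline and post-baseline, with change and percent change.

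On missing items in general, SAP 2.7.3 says "Any missing individual items will not be imputed" and SAP 2.5.3 says they are treated as missing data. Both send the reader to the Appendix for the handling. SAP 2.7.3 lists the DLQI among the questionnaires in which questions may be skipped.

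**The concern.** A score of 0 for one blank among ten items moves a 0–30 total by at most 3 points, and the total is dropped once a second item is blank. The same convention in a one-question subsection makes the blank the entire score, and 0 is the value that defines response. A patient who gave no answer is then counted as a treatment success, in a rate reported with a 95% CI.

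These zeros are not missing values. They bypass LOCF and do not enter the planned percentage of scores imputed by LOCF. At stake are the subsection response rates by visit and subpopulation, and the subsection means that accompany them.

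**Working it through.** The documents state no figure for this rule, so there is nothing to reproduce. The check has three steps.

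**Step 1: apply SAP 5.4.1 literally.** Unanswered = 0; total missing if more than one question is unanswered; subsection = plain sum; response = sum equal to 0. Every question not mentioned in a row is set to the worst score, 3.

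| Pattern | Total | Subsection score | Counted as response of 0? |
|---|---|---|---|
| Question 7 blank | 9 × 3 = 27 | Work and school = 0 | Yes |
| Question 10 blank | 9 × 3 = 27 | Treatment = 0 | Yes |
| Question 1 blank, question 2 answered 0 | 8 × 3 = 24 | Symptoms and feelings = 0 | Yes |
| Both questions of a two-question subsection blank | Missing | 0 | Yes, if the missing rule covers only the total |

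The first three rows have a single blank, so the more-than-one rule is never triggered, whatever its scope.

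**Step 2: effect on a response rate.** Let m be the share of patients whose subsection is blank and p the true rate of 0, taken to be the same in those who answered and those who did not.

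Reported rate = m + (1 − m)p, so inflation = m + (1 − m)p − p = m(1 − p).

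| m (assumed) | p = 70% | p = 50% |
|---|---|---|
| 1% | 0.01 × 0.30 = 0.3 points | 0.01 × 0.50 = 0.5 points |
| 5% | 0.05 × 0.30 = 1.5 points | 0.05 × 0.50 = 2.5 points |

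The expression cannot be negative. For a two-question subsection with one blank and one 0 it keeps the same form, with m the share showing that pattern and p the chance that the blank question would have been 0.

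**Step 3: effect on change from baseline.** SAP 2.1.1 defines change as post-baseline minus baseline. Take a hypothetical patient whose true Treatment scores are 3 at Baseline and 1 at Week 16, a change of 1 − 3 = −2.

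- Blank at Week 16: 0 − 3 = −3, so improvement is overstated.
- Blank at Baseline: 1 − 0 = +1, so improvement is recorded as worsening.

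At a single visit the false zero can only lower the score. For change scores the direction depends on when the blank occurs.

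**The case against.** **The general missing-item statements.** SAP 2.5.3 and 2.7.3 say missing items are missing or not imputed, which might seem to settle the matter. A reader might equally infer that 5.4.1 flatly contradicts them. Neither follows. Both sections defer to the Appendix, so 5.4.1 is the operative rule. The texts are in tension, and the general statements do not supply a subsection rule.

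**Scope of the more-than-one rule.** It could be read as covering the whole form, so that a wholly blank form, or a two-question subsection with both items blank, would not be scored. Its position, after the 0–30 total and before the subsections, points to the total only, but the text does not settle it. It would therefore be too strong to say that a blank form certainly counts as a response in all six subsections. This reading does not rescue the single-blank cases.

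**Disclosure.** SAP 2.5.3 and 2.7.3 plan to present the percentage of missing DLQI items over visits, so blanks would be visible. That stands, but the table does not correct the rates.

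**Frequency.** Protocol 6.6.1 has the study coordinator check questionnaires for completeness and encourage patients to fill gaps, and a not-relevant answer is already available. Blanks should be few. No document supports a particular value of m.

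**Importance.** Subsection response is not named in the study objectives. Protocol 6.6.1.2 says only that subscales may be analysed separately, and all analyses are descriptive. This limits the weight of the point but does not make the rule right.

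The SAP's handling of its other questionnaires suggests an oversight. The TSQM has a missing rule for each scale, the HAQ-DI uses answered items and limits missing categories, the PBI treats unanswered items as missing, and the EQ-5D index is not calculated if a dimension is missing.

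**Conclusion.** The rule is wrong as written for the subsections. A skipped question 7 or 10, or one blank beside one 0 in a two-question subsection, counts as a response of 0. For a two-question subsection with both items blank, the same holds unless the more-than-one rule is taken to cover the whole form.

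At any visit the subsection response rates can only be pushed up. The size is 0.3 to 0.5 points at an assumed 1% blank and 1.5 to 2.5 points at 5%, for true rates of 70% to 50%. These figures assume equal true rates in patients with and without blanks. They measure the distance from the true rate. They are not the exact shift the fix would produce, because under LOCF a patient with an earlier subsection score of 0 remains a responder.

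Two broader conclusions might be inferred and are not supported. Change from baseline is not always biased toward improvement, since a blank at Baseline works the other way. The primary DLQI 0/1 endpoint is not touched by the subsection gap, because the total has its own missing rule. The point is confined to descriptive secondary summaries and should be corrected before they are produced.

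**What to change.** Add to SAP 5.4.1:

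> A DLQI subsection score is set to missing if any of its own questions is unanswered; missing post-baseline subsection scores are then handled by LOCF as in Section 2.7.3. The score of 0 for an unanswered question applies to the total score only. Question 7 answered No with its second part blank keeps its stated score of 0.

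The rule should look only at a subsection's own questions. Setting a subsection to missing because of blanks elsewhere on the form would discard complete data: blanks in questions 7 and 10, for example, would remove a fully answered Symptoms and feelings score.

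The cost is a few lines of SAP text and one programming condition. Subsection response rates may fall slightly, and a few more subsection values will be imputed and shown as such. The total score and the primary analysis are unchanged.
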